3.2.3 Exploratory Objective Estimands

The estimands corresponding to the exploratory objectives are shown in Table 3.

Table 3 Exploratory Objective Estimands

| Objective 1 | Mean reduction from the OP in the number of migraine days per month and number of headache days per month by pain intensity (total; moderate or severe) in each month and over the entire DBT Phase | |
|----------------------------|---|--|
| Efficacy Endpoint | Mean changes from the OP in the number of migraine days per month and number of headache days per month during DBT (1) over time by month and (2) overall DBT, by pain intensity (total; moderate or severe) | |
| Summary | Mean changes from the OP by treatment group using descriptive statistics and linear mixed effects model with repeated measures, and difference between treatment groups from model for the migraine analysis set | |
| | Study drug discontinuation: hypothetical strategy | |
| | Nonstudy prophylactic migraine medication use: treatment policy strategy | |
| Intercurrent Events | Nonstudy acute migraine-specific medication use: composite strategy | |
| intercurrent Events | Use of nonstudy other medication to treat headache (migraine or nonmigraine) or aura: treatment policy strategy for migraine days; composite strategy for headache days | |
| Objective 2 | Proportions of subjects with ≥ 50% reduction, ≥ 75% reduction, and 100% reduction from the OP in the number of migraine days per month and number of headache days per month by pain intensity (total; moderate or severe) in each month and over the entire DBT Phase | |
| Efficacy Endpoint | Proportions of subjects with $\geq 50\%$ reduction, $\geq 75\%$ reduction, and 100% reduction from the OP in the number of migraine days per month and number of headache days per month during DBT (1) over time by month and (2) overall DBT, by pain intensity (total; moderate or severe) | |
| Summary | Percentages by treatment group, and difference in percentages between treatment groups using Mantel-Haenszel risk estimation for the migraine analysis set | |
| | Study drug discontinuation: composite strategy | |
| | Nonstudy prophylactic migraine medication use: treatment policy strategy | |
| Intercurrent Events | Nonstudy acute migraine-specific medication use: composite strategy | |
| Thereas Events | Use of nonstudy other medication to treat headache (migraine or nonmigraine) or aura: treatment policy strategy for migraine days; composite strategy for headache days | |
| Objective 3 | Mean reduction from the OP in the number of migraine days per week and number of headache days per week by pain intensity (total; moderate or severe) in each week of the first 4 weeks of the DBT Phase | |
| Efficacy Endpoint | Mean changes from the OP in the number of migraine days per week and number of headache days per week over time by week during the first 4 weeks of DBT, by pain intensity (total; moderate or severe) | |
| Summary | Mean changes from the OP by treatment group using descriptive statistics and linear mixed effects model with repeated measures, and difference between treatment groups from model for the first month migraine analysis set | |
| | Study drug discontinuation: hypothetical strategy | |
| Intercurrent Events | Nonstudy prophylactic migraine medication use: treatment policy strategy | |
| | Nonstudy acute migraine-specific medication use: composite strategy | |

| | Use of nonstudy other medication to treat headache (migraine or nonmigraine) or aura: treatment policy strategy for migraine days; composite strategy for headache days | | |
|----------------------------|--|--|--|
| Objective 4 | Proportions of subjects with $\geq 50\%$ reduction from the OP in the number of migraine days per week and number of headache days per week by pain intensity (total; moderate or severe) in each week of the first 4 weeks of the DBT Phase | | |
| Efficacy Endpoint | Proportions of subjects with $\geq 50\%$ reduction from the OP in the number of migraine days per week and number of headache days per week over time by week during the first 4 weeks of DBT, by pain intensity (total; moderate or severe) | | |
| Summary | Percentages by treatment group, and difference in percentages between treatment groups using Mantel-Haenszel risk estimation for the first month migraine analysis se | | |
| | Study drug discontinuation: composite strategy | | |
| | Nonstudy prophylactic migraine medication use: treatment policy strategy | | |
| Intercurrent Events | Nonstudy acute migraine-specific medication use: composite strategy | | |
| intercurrent Events | Use of nonstudy other medication to treat headache (migraine or nonmigraine) or aura: treatment policy strategy for migraine days; composite strategy for headache days | | |
| Objective 5 | Proportions of subjects with a migraine day and headache day by pain intensity (total; moderate or severe) on each day of the first week of the DBT Phase | | |
| Efficacy Endpoint | Proportions of subjects with a migraine day and headache day on each day of the first week of the DBT Phase, by pain intensity (total; moderate or severe) | | |
| Summary | Percentages by treatment group, and difference in percentages between treatment groups using Mantel-Haenszel risk estimation for the first week treated migraine analysis set | | |
| | Study drug discontinuation: not applicable due to definition of the first week treated migraine analysis set | | |
| | Nonstudy prophylactic migraine medication use: treatment policy strategy | | |
| Intercurrent Events | Nonstudy acute migraine-specific medication use: composite strategy | | |
| | Use of nonstudy other medication to treat headache (migraine or nonmigraine) or aura: treatment policy strategy for migraine days; composite strategy for headache days | | |
| Objective 6 | Mean number of acute migraine-specific medication days per month in each month and over the entire DBT Phase | | |
| Efficacy Endpoint | Mean number of acute migraine-specific medication days per month during DBT (1) over time by month and (2) overall DBT | | |
| Summary | Mean values by treatment group using descriptive statistics and linear mixed effects model with repeated measures, and difference between treatment groups from model for the migraine analysis set | | |
| | Study drug discontinuation: hypothetical strategy | | |
| | Nonstudy prophylactic migraine medication use: treatment policy strategy | | |
| Intercurrent Events | Nonstudy acute migraine-specific medication use: not applicable | | |
| | Use of nonstudy other medication to treat headache (migraine or nonmigraine) or aura: treatment policy strategy | | |

| Objective 7 | Mean number of acute migraine medication days per month in each month and over the entire DBT Phase | |
|-------------------------------|---|--|
| Efficacy Endpoint | Mean number of acute migraine medication days per month during DBT (1) over time by month and (2) overall DBT | |
| Summary | Mean values by treatment group using descriptive statistics and linear mixed effects model with repeated measures, and difference between treatment groups from model for the migraine analysis set | |
| | Study drug discontinuation: hypothetical strategy | |
| | Nonstudy prophylactic migraine medication use: treatment policy strategy | |
| Intercurrent Events | Nonstudy acute migraine-specific medication use: not applicable | |
| | Use of nonstudy other medication to treat headache (migraine or nonmigraine) or aura: not applicable | |
| Objective 8 | Frequency of LFT elevations based on fold changes above ULN in subjects treated with rimegepant during the DBT and OLE Phases | |
| Safety Endpoint | Number and percentage of subjects with LFT elevations (ALT, AST, or TBL) based on fold changes above ULN on treatment | |
| Summary | Frequency by treatment group for the DB and OL rimegepant, and DB or OL rimegepant safety analysis sets with LFT data on treatment | |
| | Study drug discontinuation: while-on-treatment strategy | |
| Intercurrent Events | Nonstudy prophylactic migraine medication use: treatment policy strategy | |
| | Nonstudy acute migraine-specific medication use: treatment policy strategy | |
| | Use of nonstudy other medication to treat headache (migraine or nonmigraine) or aura: treatment policy strategy | |
| Objective 9 | Frequency of ALT or AST > 3x ULN in temporal association with nausea, vomiting, anorexia, abdominal pain or fatigue in subjects treated with rimegepant during the DBT and OLE Phases | |
| Safety Endpoint | Number and percentage of subjects in the DBT safety analysis set with ALT or AST > 3x ULN concurrent with nausea, vomiting, anorexia, abdominal pain or fatigue on treatment | |
| Summary | Frequency by treatment group for the DB and OL rimegepant safety analysis sets with LFT data on treatment | |
| | Study drug discontinuation: while-on-treatment strategy | |
| | Nonstudy prophylactic migraine medication use: treatment policy strategy | |
| Intercurrent Events | Nonstudy acute migraine-specific medication use: treatment policy strategy | |
| | Use of nonstudy other medication to treat headache (migraine or nonmigraine) or aura: treatment policy strategy | |
| Objective 10 | Mean changes from baseline in MSQ domain scores during the DBT and OLE Phases | |
| Outcomes Research Endpoint | Mean changes from baseline in the (1) MSQ restrictive role function, preventive role function, and emotional function domain scores at Week 12 of the DBT Phase and Week 24 of the OLE Phase | |

| Summary | (1) Mean changes from baseline at Week 12 in each domain score by treatment group using descriptive statistics and linear model, and difference between treatment groups from model for the DBT efficacy analysis set; (2) mean changes from baseline at Week 24 in each domain score by treatment group using descriptive statistics for the DBT efficacy analysis set | |
|-------------------------------|---|--|
| | Study drug discontinuation: treatment policy strategy | |
| | Nonstudy prophylactic migraine medication use: treatment policy strategy | |
| Intercurrent Events | Nonstudy acute migraine-specific medication use: treatment policy strategy | |
| | Use of nonstudy other medication to treat headache (migraine or nonmigraine) or aura: treatment policy strategy | |
| Objective 11 | SM scale during the DBT and OLE Phases | |
| Outcomes Research Endpoint | Number and percentage of subjects in each of 7 satisfaction categories (completely satisfied to completely dissatisfied) of study medication at Weeks 12 and 24 | |
| Summary | Frequency over time by treatment group for the DBT efficacy analysis set with SM data | |
| | Study drug discontinuation: treatment policy strategy | |
| | Nonstudy prophylactic migraine medication use: treatment policy strategy | |
| Intercurrent Events | Nonstudy acute migraine-specific medication use: treatment policy strategy | |
| | Use of nonstudy other medication to treat headache (migraine or nonmigraine) or aura: treatment policy strategy | |
| Objective 12 | CGI-c scale during the DBT and OLE Phases | |
| Outcomes Research Endpoint | Number and percentage of subjects in each of 7 improvement categories (very much improved to very much worse) relative to investigator's past experience with other patients with the same diagnosis at Weeks 12 and 24 | |
| Summary | Frequency over time by treatment group for the DBT efficacy analysis set with CGI-c data | |
| | Study drug discontinuation: treatment policy strategy | |
| | Nonstudy prophylactic migraine medication use: treatment policy strategy | |
| Intercurrent Events | Nonstudy acute migraine-specific medication use: treatment policy strategy | |
| | Use of nonstudy other medication to treat headache (migraine or nonmigraine) or aura: treatment policy strategy | |

4 ANALYSIS SETS, TREATMENT GROUPS, AND SUBGROUPS

4.1 Analysis Sets

The following analysis sets are evaluated and used for presentation and analysis of the data:

• Enrolled: Subjects who sign an informed consent form and are assigned a subject identification number, i.e., nonmissing informed consent date. This analysis set is used mainly to assess study population and in by-subject listings.

- Full: subjects in the enrolled analysis set who receive a randomized treatment assignment from the IWRS, i.e., nonmissing IWRS randomization date. This analysis set is used mainly to assess study population.
- Safety: subjects in the enrolled analysis set who take ≥ 1 dose of study drug (DB rimegepant, OL rimegepant, or placebo), i.e., nonmissing study drug start date. This analysis set is used to assess study population and produce select by-subject listings.
 - OBT safety: subjects in the safety analysis set who take ≥ 1 dose of DB study drug (rimegepant or placebo), i.e., nonmissing DB study drug start date. This analysis set is used to assess study population, exposure, and on-DBT safety.
 - OL rimegepant safety: subjects in the safety analysis set who take ≥ 1 dose of OL rimegepant, i.e., nonmissing OL rimegepant start date. This analysis set is used to assess study population, exposure, and on-OL rimegepant safety.
 - Interim safety: subjects in the OL rimegepant safety analysis set with OL rimegepant start date DB study drug last date > 7 days. This analysis set is used to assess post-DBT pre-OL rimegepant safety.
 - Ouble-blind (DB) or OL rimegepant safety: subjects in the safety analysis set who take ≥ 1 dose of DB or OL rimegepant, i.e., nonmissing DB or OL rimegepant start date. This analysis set is used to assess study population, exposure, and on-DB or OL rimegepant safety.
 - o Follow-up safety: subjects in the safety analysis set whose last contact date is in the follow-up safety analysis period. This analysis set is used to assess follow-up safety.
- DBT efficacy: subjects in the full analysis set who are randomized only once and take ≥ 1 dose of DB study drug (rimegepant or placebo). This analysis set is used to analyze outcomes research during the DBT Phase.
 - O Migraine: subjects in the DBT efficacy analysis set with ≥ 14 days of eDiary efficacy data (not necessarily consecutive) in both the OP and ≥ 1 month (4-week interval) in the DBT Phase (see Section 6.3.1). This analysis set is used to assess migraine days, acute migraine-specific medication days, acute migraine medication days, and headache days.
 - o First month migraine: subjects in the DBT efficacy analysis set with ≥ 24 days of eDiary efficacy data (not necessarily consecutive) in both the OP and in first month (4-week interval) of the DBT Phase (see Section 6.3.3.3). This analysis set is used to assess efficacy endpoints per week.
 - o First week treated migraine: subjects in the DBT efficacy analysis set with (1) ≥ 24 days of eDiary efficacy data in the OP (not necessarily consecutive), (2) 7 consecutive days of eDiary efficacy data in the first week of the DBT Phase, and (3) 7 consecutive days of DB study drug dosing in the first week of the DBT Phase (see Section 6.3.3.5). This analysis set is used to assess efficacy endpoints per day.

See Section 7.1 for derived dates and Section 7.2 for analysis periods.

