3.2 Estimands

An estimand is the target of estimation to address the scientific question of interest posed by a study objective. The 4 attributes of an estimand include the population of interest, endpoint of interest, summary of the endpoint, and specification of how intercurrent events are reflected in the scientific question of interest.

For all objectives, the population of interest is defined through appropriate inclusion/exclusion criteria to reflect the targeted patient population for approval. Refer to the protocol for inclusion/exclusion criteria.

Intercurrent Events

Intercurrent events are those that occur after treatment initiation and either preclude observation of the endpoint or affect its interpretation.

Study drug discontinuation before the time point of interest defining the endpoint is considered an intercurrent event.

- For efficacy objectives assessed with a continuous endpoint during the DBT Phase, study drug discontinuation is handled with a "hypothetical strategy," i.e., the hypothetical scenario is that had subjects not discontinued DB study drug, their efficacy would have been similar to the efficacy of subjects from the same treatment group and randomization stratum who did not discontinue DB study drug. All observed values of the endpoint of interest are excluded after DB study drug discontinuation (see Section 7.2), and statistical methods are used to estimate the treatment effect that would have been seen had the intercurrent event not occurred.
- For efficacy objectives assessed with a binary endpoint during the DBT Phase, DB study drug discontinuation is handled with a "composite strategy," i.e., the occurrence of the intercurrent event is integrated as a component of the endpoint. All observed values of the endpoint of interest are excluded after DB study drug discontinuation (see Section 7.2), and subjects with missing data are considered failures.
- For safety objectives, study drug discontinuation is handled with a "while-on-treatment strategy," i.e., response to treatment prior to the occurrence of the intercurrent event of

interest, such that all observed values of the endpoint of interest are used prior to study drug discontinuation plus 7 days (see Section 7.2 and the Core SAP).

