For each pain intensity (total; moderate or severe) and select percentage reduction ($\geq 50\%$, \geq 75%, and 100%), the percentages of subjects with reduction in the number of headache days per month are compared between each rimegepant treatment group and placebo using Mantel-Haenszel risk estimation with stratification by randomization stratum (yes, no). The table has the same format as the one described in Section 6.3.2.1. Results support exploratory objective #2.

6.3.3.3 Migraine Days per Week and Headache Days per Week Changes From the OP Over Time in the First Month on DBT

The number of migraine days per week in the first month (Weeks 1 to 4) of the DBT Phase is examined relative to the number of migraine days per week in the OP for the first month migraine analysis set, i.e., subjects in the DBT efficacy analysis set with ≥ 24 days of eDiary efficacy data (not necessarily consecutive) in both the OP analysis period and first month of the on-DBT efficacy analysis period.

Weeks 1 to 4 of the DBT Phase are defined as follows:

- Week 1: study days 1 to 7
- Week 2: study days 8 to 14
- Week 3: study days 15 to 21
- Week 4: study days 22 to 28.

See Sections 7.2 and 7.3 for the definition of analysis periods and study days used to define analysis visit windows.

Analyses are based on the first month migraine analysis set using eDiary efficacy data dates in the OP and on-DBT efficacy analysis periods.

The number of migraine days per week is prorated to 7 days and derived as follows:

- OP: 7 × (total number of migraine days in the OP analysis period)/(total number of eDiary efficacy data days in the OP analysis period)
- Week (7-day interval) of the on-DBT efficacy analysis period: $7 \times$ (total number of migraine days in the week)/(total number of eDiary efficacy data days in the week).

The number of headache days per week is derived analogously.

Descriptive Analyses

The table of values and changes (both absolute and percent) from the OP in the number of migraine days per week in the first month (Weeks 1 to 4) of the DBT Phase is provided, and summarizes parameters descriptively as continuous variables (including 2-sided normal 97.5% CIs for mean change) by treatment group and pain intensity (total; moderate or severe). In the percent change analyses, subjects must also have ≥ 1 migraine day of appropriate intensity (absolute not prorated) in the OP analysis period to be included.

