The table of values and changes from the OP in number of headache days per week in the first month of the DBT Phase is provided analogously.

Treatment Group Comparisons

Treatment groups are compared using a linear mixed effects model with repeated measures and the following attributes:

- Variables: change from the OP in number of total migraine days per week as the dependent variable; number of total migraine days per week in the OP as a covariate; treatment group, randomization stratum, week (i.e., Weeks 1 to 4 of the DBT Phase), and the week-by-treatment group interaction as fixed effects.
- Covariance structure for repeated measures accounting for within-subject correlated errors: See Section 6.3.1.3.
- SE estimation method: See Section 6.3.1.3.

The table displays the following model estimates:

- LSM change from OP, SE, and 97.5% CI by week for each treatment group
- Difference in LSM changes from OP between each rimegepant treatment group and placebo (rimegepant_i placebo; i = 1 and 2), SE, 97.5% CI, and p-value for each week.

See Section 9.3.1 for example SAS code. Model estimates by randomization stratum (yes, no) are presented in the same table, using additional linear mixed effects models that exclude randomization stratum as a fixed effect.

These analyses are repeated for moderate or severe pain intensity. All variables in the model are the same, except (1) change from the OP in number of moderate or severe migraine days per week is the dependent variable, and (2) number of moderate or severe migraine days per week in the OP is the covariate. The corresponding table has the same format.

All analyses described above are performed analogously for headache days per week.

Results support exploratory objective #3.

6.3.3.4 Percentages of Subjects With Reductions in Numbers of Migraine Days per Week and Headache Days per Week Over Time in the First Month on DBT

Analyses are based on the first month migraine analysis set with eDiary efficacy data dates in the OP and on-DBT efficacy analysis periods (see Section 7.2).

In analyses of migraine days per week, subjects must (1) achieve the reduction criterion from OP in the number of migraine days in the specified week, and (2) have ≥ 1 migraine day (absolute not prorated) of appropriate pain intensity in the OP analysis period to be classified as responders in the specified week. Otherwise, subjects are classified as failures in the specified week.

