Analyses of headache days per week are defined analogously.

Treatment Group Comparisons

For each pain intensity (total; moderate or severe), the percentages of subjects with $\geq 50\%$ reduction in the number of migraine days per week are compared between each rimegepant treatment group and placebo using Mantel-Haenszel risk estimation with stratification by randomization stratum (yes, no). Percentages are calculated against the number of subjects in the first month migraine analysis set.

The table displays the following statistics at each week of the DBT Phase by pain intensity:

- Response rate (i.e., "n/N" and percentage), ASE, and 97.5% CI for each treatment group
- Stratified percentage difference between each rimegepant treatment group and placebo (rimegepant_i placebo; i = 1 and 2), ASE, 97.5% CI, and p-value
- Response rate (i.e., "n/N" and percentage), ASE, and 97.5% CI by randomization stratum for each treatment group and placebo
- Percentage difference between each rimegepant treatment group and placebo (rimegepant_i placebo; i = 1 and 2), ASE, 97.5% CI, and p-value by randomization stratum.

All analyses described above are performed analogously for headache days per week.

Results support exploratory objective #4.

6.3.3.5 Percentages of Subjects With Migraine Days and Headache Days Over Time in the First Week on DBT

Analyses are based on the first week treated migraine analysis set, i.e., subjects in the DBT efficacy analysis set with $(1) \ge 24$ days of eDiary efficacy data (not necessarily consecutive) in the OP analysis period, (2) 7 consecutive days of eDiary efficacy data in the first week (i.e., study days 1 through 7) of the DBT efficacy analysis period, and (3) 7 consecutive days of DB study drug dosing in the first week of the DBT efficacy analysis period (see Section 9.4).

Treatment Group Comparisons

Analyses are based on the first week migraine analysis set with eDiary efficacy data dates in the OP and on-DBT efficacy analysis periods (see Section 7.2).

For each pain intensity (total; moderate or severe), the percentages of subjects with a migraine day are compared between each rimegepant treatment group and placebo using Mantel-Haenszel risk estimation with stratification by randomization stratum (yes, no) at study days 1 through 7 of the DBT Phase. Percentages are calculated against the number of subjects in the first week treated migraine analysis set.

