7.2 Analysis Periods

Measurements are slotted into analysis periods based on comparing measurement dates to analysis period reference dates (time is not applicable).

Analysis periods are defined according to endpoints as follows:

• eDiary efficacy endpoints (migraine days, acute migraine-specific medication days, acute migraine medication days, headache days)

- OP: eDiary efficacy data date on or after the OP start date through the OP end date. Note that this is a subset of the pretreatment analysis period.
- 28-day OP: eDiary efficacy data date on or after the OP start date through the earlier of {OP start date + 27 days; OP end date}. Note that this is a subset of the OP analysis period, and is used only to assess efficacy data issues during the OP as relevant protocol deviations.
- o On-DBT efficacy:
 - If the DB study drug last date or OL rimegepant start date is not missing: eDiary efficacy date on or after the DB study drug start date through the earlier of {DB study drug last date; OL rimegepant start date 1 day}
 - If the DB study drug last date and OL rimegepant start date are both missing: eDiary efficacy data date on or after the DB study drug start date

This period is used to assess efficacy during the DBT Phase.

- Pretreatment characteristics and safety endpoints *
 - Pretreatment: This period is used to derive baseline values
 - On-DBT safety: This period is used to assess safety endpoints on DBT for the DBT safety analysis set.
 - Post-DBT pre-OL rimegepant safety: This period is used to assess safety endpoints during the interim period (i.e., post-DBT pre-OL rimegepant) for the interim safety analysis set.
 - On-OL rimegepant safety: This period is used to assess safety endpoints on OL rimegepant for the OL rimegepant safety analysis set.
 - On-DB or OL rimegepant safety: This period is used to assess safety endpoints on DB or OL rimegepant for the DB or OL rimegepant safety analysis set.
 - On-treatment safety: This period is used to derive analysis visit windows for slotting
 measurements and may also be used to assess blinded safety endpoints on treatment in an
 integrated safety report, as needed.
 - Follow-up safety: This period is used to assess safety endpoints during follow-up for the follow-up safety analysis set.
- Outcomes research endpoints (MSQoL, SM, CGI-c) *
 - DBT outcomes research: This period is used to assess outcomes research endpoints during the DBT Phase for the DBT efficacy analysis set.

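### The weekly analyses (exploratory objectives 3 and 4) use a set selected on Month 1 on-treatment diary completion, so the discontinuation strategies in Table 3 have nothing to act on

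*SAP*

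**What the plan says.** Exploratory objective 3 is the change from the Observation Phase in migraine and headache days in each of Weeks 1–4. Objective 4 is the proportion with at least a 50% reduction in each of those weeks.

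- **Set.** Table 3 (SAP 3.2.3) gives the objective 3 summary as the "difference between treatment groups from model for the first month migraine analysis set", and objective 4 uses the same set. SAP 4.1 defines it: "First month migraine: subjects in the DBT efficacy analysis set with ≥ 24 days of eDiary efficacy data". SAP 6.3.3.3 says the threshold must be met "in both the OP analysis period and first month of the on-DBT efficacy analysis period".
- **On-treatment window.** SAP 7.2 counts an "eDiary efficacy date on or after the DB study drug start date through the earlier of" the last double-blind dose date and the day before open-label start.
- **Objective 4 scoring.** In SAP 6.3.3.4 a responder must reach the reduction in that week and have at least one migraine day in the Observation Phase. "Otherwise, subjects are classified as failures in the specified week". On the denominator, "Percentages are calculated against the number of subjects in the" first month migraine analysis set.
- **Discontinuation.** Table 3 assigns a hypothetical strategy to objective 3 and a composite strategy to objective 4. SAP 3.2 says for both types of endpoint: "All observed values of the endpoint of interest are excluded after DB study drug discontinuation". For binary endpoints, missing data then count as failure.
- **Objective 5.** For the daily analyses in the first week, Table 3 marks discontinuation as not applicable because of how that set is defined. Objectives 3 and 4 carry no such note.

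**The concern.** The Observation Phase half of the criterion is fixed before randomisation and matches the protocol's entry rule (Protocol 4.3.2.1 and 5.3), so it does no harm. The Month 1 half depends on staying on drug and completing the diary, both of which happen after randomisation and can differ by arm.

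Two things are at stake. First, the SAP states estimand strategies that its own analysis set prevents from operating, so a reader of Table 3 would be misled about how early stoppers are treated. Second, the weekly tables report differences, 97.5% CIs and p-values for subjects who stayed on treatment and kept a diary for nearly a month. If stopping is unequal between arms, those differences mix drug effect with selection. The jump-to-reference and tipping-point analyses cover only the primary endpoint, so no planned sensitivity analysis would show this.

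**Working it through.** **The plan's own figure.** The SAP states no size, power or exclusion rate for the weekly set. Its only related figure is power on the primary endpoint (SAP 5): 200 per arm, 1.1-day effect, SD 3.5, two-sided alpha 0.025. The SE is 3.5 × √(2/200) = 0.35 and the ratio is 1.1/0.35 = 3.14, giving power 0.816, in line with the stated 80%. It does not bear on the weekly set.

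**Step 1: who can enter.** On-treatment diary days cannot exceed the last-dose day. Month 1 has 28 days ("Week 4: study days 22 to 28" closes it). The migraine set needs at least 14 days in some month.

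| Last dose | Most diary days possible | Weekly set (≥24) | Main migraine set (≥14) |
|---|---|---|---|
| Day 7 | 7 | no | no |
| Day 14 | 14 | no | possible |
| Day 21 | 21 | no | possible |
| Day 23 | 23 | no | possible |
| Day 24 | 24 | only with no missed day | possible |

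A subject who stops on Day 21 with three complete diary weeks contributes nothing to Weeks 1, 2 or 3.

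**Step 2: can a weekly value be missing inside the set?** A member misses at most 28 − 24 = 4 days. Even if all 4 fall in one week, 7 − 4 = 3 remain, so a prorated value always exists. A member whose last dose is on Day 24 is scored in Week 4 on Days 22–24, not as a failure. Hence:

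- Objective 4: no discontinuation can become a failure through missing data.
- Objective 3: every subject in the model has all four weekly values. Early stoppers' pre-discontinuation weeks, which SAP 3.2 does not exclude, are lost.

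**Step 3: loss from the diary alone.** Assume independent daily completion c while on drug. P(at least 24 of 28) is 0.988 at c = 95%, 0.858 at 90%, 0.587 at 85% and 0.315 at 80%. P(at least 14 of 28) is about 1.00 throughout. These completion rates are assumptions.

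**Step 4: possible size, objective 4 (all rates assumed).** Suppose weekly response among those kept is 45% on rimegepant and 35% on placebo, a 10.0-point difference. If a fraction e₁ (rimegepant) and e₂ (placebo) is excluded and *every* excluded subject is a failure in that week, the difference is 45(1 − e₁) − 35(1 − e₂):

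- 5% and 5%: 42.75 − 33.25 = 9.5
- 8% and 4%: 41.4 − 33.6 = 7.8
- 10% and 5%: 40.5 − 33.25 = 7.25
- 5% and 10%: 42.75 − 31.5 = 11.25

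The first case only rescales the difference; the last shows the direction reversing. With no true difference (50% in both arms among those kept), the same rule gives 50 × [(1 − e₁) − (1 − e₂)]: −1.0 point at 5% vs 3%, −2.5 at 10% vs 5%, and 0 at 3% vs 3%.

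These figures apply only to a week in which all excluded subjects would be failures. With a minimum of 4 of 7 diary days, that holds in Week 4 for anyone with a last dose by Day 23, who has at most Days 22 and 23. It does not hold in Weeks 1–3 for weeks with enough diary days: a full diary to Day 20 gives 7, 7 and 6 days. Nor does it generally hold for subjects still on drug who missed scattered diary days.

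**Step 5: possible size, objective 3 (assumed).** Assume no true effect, and that stoppers average k migraine days per week more than stayers. Stayers then lie k × d below their arm mean, where d is the arm's stopping rate, and the filtered difference is −k(d₁ − d₂). For k = 0.5 to 1.0 this is −0.025 to −0.05 days per week at 10% vs 5%, and −0.05 to −0.10 at 15% vs 5%. The sign reverses if placebo subjects stop more.

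**The case against.** Nothing confirmatory is touched. SAP 5 leaves exploratory endpoints outside multiplicity control and calls their p-values descriptive. The Weeks 1–4 effect is also a secondary endpoint in the testing hierarchy, estimated from the primary model in the less restrictive migraine set, where a subject stopping on Days 14–23 with enough diary days contributes. A reader might infer that every claim about early effect rests on the 24-day set; that does not follow. All of this stands.

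The threshold also has a purpose. Weekly counts are prorated with no per-week minimum, and the 24-day rule is what guarantees at least 3 diary days behind each value. That stands as a reason to replace the rule rather than delete it. The replacement minimum is a choice that the documents do not settle.

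For objective 3 one can argue that the hypothetical strategy in SAP 3.2 already assumes stoppers would have done as well as stayers in the same arm and stratum, so dropping them is consistent with it. That stands in part. But SAP 3.2 excludes only values after discontinuation, whereas the set also discards those before it. For objective 4 the argument gives no help, since composite means counting stoppers as failures.

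Finally, a reader might infer that randomised groups are no longer compared. That is too strong: as-randomized labels are kept (SAP 4.2), and the main migraine set is also selected on post-randomisation diary data, only much less severely.

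**Conclusion.** The conflict is real and follows from SAP 4.1, 6.3.3.3, 6.3.3.4 and 7.2 read together. The Month 1 diary filter removes early stoppers and poor diary completers with all their observed weeks, and leaves the Table 3 discontinuation strategies for objectives 3 and 4 empty. The SAP recognises this consequence for objective 5 but not here.

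The effect on results cannot be sized. A reader might infer that weekly effects will be overstated by some 2 to 3 points. The documents do not support that: they give neither early-stopping rates nor weekly response rates. The bias favours rimegepant only if more rimegepant than placebo subjects stop early, and the Step 4 figures are an assumed bound for weeks in which all excluded subjects would be failures. Primary and key secondary conclusions, including the Weeks 1–4 secondary endpoint, are unaffected. This is a change worth making to exploratory tables, not a threat to the trial's main inference.

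**What to change.** - **Set.** Analyse objectives 3 and 4 in the DBT efficacy analysis set, limited to subjects with an evaluable Observation Phase baseline. Keep the pre-randomisation 24-day requirement, or use the 14-day rule of SAP 6.3.1. A baseline limit must be stated, because the DBT efficacy set has none and SAP 9.1 anticipates subjects with 23 or fewer Observation Phase diary days as deviations.
- **Evaluability.** Replace the Month 1 24-day filter with a per-week minimum, for example 4 of 7 diary days.
- **Objective 4.** Count weeks below the minimum, including those emptied by discontinuation, as failures, with all subjects in the denominator. SAP 6.3.2.1 already does this for monthly responders with fewer than 14 diary days.
- **Objective 3.** Leave such weeks missing in the mixed model, so that earlier observed weeks are used.
- **Supplementary.** Keep the present set as a supplementary analysis.

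If the set is not changed, Table 3 should at least say for objectives 3 and 4, as it does for objective 5, that the set definition leaves discontinuation with no role.

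The cost is SAP wording, some reprogramming and a rerun of exploratory tables. Response rates would be slightly lower.
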